1. INTRODUCTION

1.1 Background

Current assessments of lung inflammation for asthmatics and chronic obstructive pulmonary disease (COPD) are mainly based on patient symptoms and simple spirometry tests. Unfortunately, these features are not directly correlated to eosinophilic lung inflammation. Consequently, clinicians cannot always predict the degree of lower airway inflammation in COPD and asthmatic patients; hence it can be difficult to provide appropriate treatment. [1, 2]

More than 70% of COPD patients are underdiagnosed [3] and the 2-year mortality rate for severe COPD patients is about 50% because of exacerbation, which on average occurs 2-4 times per year [4]. Early diagnostics for COPD could not only reduce direct healthcare costs but also reduce the probability of exacerbation and mortality [5] and lead to improved patient care. COPD is a progressive disease with potential acute exacerbations; therefore, long-term monitoring must be in place to track patient condition and such monitoring requires out-patient or GP surgery visits [6].

Exhaled Breath Condensate (EBC) serves as simple and non-invasive sampling which gives access to lung chemistry, and which can potentially inform clinical decision-making. Significantly higher hydrogen peroxide (H_2O_2) concentration in EBC is found in COPD patients, (typically 0.46 μM compared to healthy control 0.2 μM [7-9]). Even higher H_2O_2 concentrations are reported for patients with exacerbation, 0.6 μM in comparison with stable COPD patients and corticosteroid-treated patients. [10, 11] Due to the limited range between stable COPD patients and COPD exacerbation, an exceptionally sensitive sensor is required for reliable diagnosis.

Most previous approaches to EBC collection have prioritised the collecting of more condensate in a shorter time and this has led to the use of a lower temperature condensation surface. However, previous EBC collector designs have not considered how EBC sample composition depends on temperature and flow rate, due to widely varying absolute values and temperature dependences of the Henry's law constants for different analytes and the enthalpy of condensation. A failure to consider quantitatively the impact of collection conditions on EBC composition has led to large, reported variations between different researchers for same health condition[7-15] which has impeded progress in this field. Here we report an approach to EBC collection aimed at optimising target analyte concentration by exploiting the differential thermodynamic and kinetic parameters involved. This model-based approach is qualitatively borne out by experimental data which we have collected by blowing compressed air through Dreschel bottles of normal saline in a water bath.

The published literature largely attributes variations in EBC analyte concentration to difference in patient physiological conditions. However, Loyola *et al.* [16] demonstrated different acetone concentrations in EBC samples at difference condensation temperatures. Zamuruyev *et al.* also showed how the amount of analyte collected varies with condensation temperature.[17]

Ferric ferrocyanide (Prussian blue (PB)) modified electrodes are well-established for both H_2O_2 and oxygen sensing [18]. Karyakin *et al.* [19] demonstrated Prussian blue H_2O_2 catalysis exhibits a

significantly higher kinetic constant compared to a platinum electrochemical sensor and that PB is comparable to horseradish peroxidase. PB modified sensors were found to have good linear range between 0.1 μM to 100 μM , with sensitivity of 0.6 $\text{A M}^{-1}\text{c m}^{-2}$ and detection limit of 0.1 μM . [20]

H_2O_2 electrochemical sensor sensitivity and stability commonly involve the use of nanoparticles of PB [21], sometimes combined with polymer reagent blends [22, 23], or conducting polymers [24-26].

We prepared an easy-to-use water dispersible poly(3,4-ethylenedioxythiophene)-poly(styrenesulfonate) potassium ferric ferrocyanide composite, cross linked with ethylene glycol and divinyl sulfone (PEDOT:PSS-PB-EG-DVS) for electrochemical H_2O_2 and oxygen detection purposes. The calibration plot shows a good linear response which easily covers the concentration ranges reported for EBC (0.1 μM to 25.6 μM) and which has a detection limit of 103 nM. We have manufactured disposable biosensors based on this technology.

Performance in artificial samples has been compared to the laboratory-based fluorometric analysis using Amplex Red, which is well-established as the gold standard for hydrogen peroxide determination in low concentration biological samples and show good agreement.

Figure 1

[figure not shown]
[figure not shown]

Figure 1: Schematic of the catalytic biosensor mechanism **B** TEM image of the electrode modifier **C** Reproducible i-V behaviour of the composite **D** condenser mechanism **E** Device schematic **F** disposable biosensor strip **G** Generation of test specimens for laboratory evaluation

Figure 2: A Biosensor coulometry data measured with PEDOT:PSS-PB-EG-DVS modified sensor against fluorometry data measured with HRP and Amplex Red. The colour strips illustrate reported physiological H_2O_2 in EBC in various patient groups [7-9, 11]. The inset demonstrates the calibration standard for HRP and Amplex Red against H_2O_2 concentration. **B.** Bland Altman analysis comparing electrochemical sensor results and the Amplex Red assay

Figure 2

1.2 Study Rationale

Following a successful pilot study and a clinical assessment in healthy volunteers (1st Clinical Evaluation) we now want to evaluate the accuracy and precision of the EBC device in patients with COPD (2nd Clinical Evaluation). We want to evaluate the reproducibility of 3 measurements a month apart in real breath samples in the same manner as the previous clinical evaluation with healthy volunteers. This will take place at the Clinical Research Facility (CRF) at the Royal Brompton Hospital. Real biological specimens are complex and there is the potential for losses of precision and accuracy. This can only be evaluated by comparison with established methodology. Secondly, whilst many reports can correctly classify COPD patients, there are substantial variations in absolute levels between researchers. We have shown with artificial samples that correcting for variations in heat and mass transport can substantially reduce these variations. Collecting replicate samples from patients with COPD will allow us to evaluate this approach in this patient group.

2. STUDY OBJECTIVES 2

The questions to answer in clinical evaluation:

1. Volume collectable in 3-5 minutes,
2. Concentration of hydrogen peroxide in COPD and healthy subjects,
3. Variability between 3 samples collected in 1 day,
4. Variability between 3 tests collected in 1st month, 2nd month and 3rd month,
5. Usefulness of standardisation method, data including breath temperature entering and leaving the device as well as breath flow rate would be collected in-situ (sensors already on device, no naked wires),
6. Usability feedback, in terms of how easy to use, to hold and to breathe through the device

The outcomes of this study will inform the design of further clinical evaluations.

3. STUDY DESIGN

Venue: This will be performed in the Clinical Respiratory Facility located at the Royal Brompton Hospital.

We aim to recruit 15 patients with COPD and 15 healthy volunteers from our database of volunteers at the royal Brompton Hospital. Our purpose with this study is to evaluate the analytical performance of the device and the data processing and consistency of measurements over a 3-month period.

Three successive measurements will be made at monthly intervals in each patient with COPD and with each healthy volunteer requiring them to visit the Hospital on three occasions. The first visit also includes screening which will take up to 1 hour.

Firstly, each potential participant will be sent a participant information sheet.

If they decide that they wish to take part in the research study, they will be asked to come to the Clinical Research Facility (CRF) at the Royal Brompton Hospital, for screening where the

research team will further explain the study to the participant. A hard copy of the participant information sheet will be provided at the appointment and participants will be encouraged to ask questions. Participants will then be presented with a consent form which they will be asked to sign before any procedures are made.

As part of screening, they will have a baseline screening questionnaire including a check of medications they are currently taking.

If the participant satisfies the screening criteria, they can then enter the study. After the consent form has been signed, participants will perform spirometry measurements prior to the following the breath collection procedures. These procedures will be performed on each study visit.

An exclusion questionnaire will be presented at the appointment.

Sample collection protocol

The handheld breath collection apparatus will be switched on by the researcher and allowed to achieve the correct temperature (1-2 minutes). A sterilised disposable plastic mouthpiece will be fitted. The participant will be asked to hold the breath collection device and breathe normally into the plastic mouthpiece for up to 5 minutes (Figure 3).

The researcher will take the instrument and remove the condensed breath sample, place it in a numbered vial and remove it for analysis in the laboratory. Ideally, three samples per participant will be collected, but the participant may withdraw consent at any point.

It will not be possible to identify the participant from the sample labelling.

The individual results of the analysis will not be made available to the participants.

The flow chart of the sample collection is shown in Figure 3 (A&B) below, C & D shows the collection device.

Participants will also be asked to fill in a short questionnaire on visit 1 related to the use of portable medical devices.

Figure 3

[figure not shown]
[figure not shown]

Figure 4 Showing 1st and 2nd Clinical Evaluation

STUDY TESTS

Apparatus during sample collection: 1 pipette, a bag of pipette tips, numbered Eppendorf vials, sterilised mouthpiece, and exhaled breath condensate (EBC) collector, 75%(v/v) aqueous ethanol solution for sterilisation of the mouthpiece and apparatus.

The following process is repeated 3 times in total to collect 3 EBC samples per participant:

1. A researcher will control device operation and sample collection.
2. The researcher switches on the device and waits until the Peltier temperature reaches 20°C, typically 1-3 minutes
3. Install the sterilised PET mouthpiece.
4. Volunteer holds the device and breathes through the PET mouthpiece normally for a maximum of 5 minutes.
5. After EBC condensation, the volunteer is to pass the device to the researcher.
6. The researcher transfers the EBC sample with pipette to vials for further analysis.
7. The EBC collector is wiped with 75% aqueous ethanol to remove remaining EBC.

Samples will be taken the Biosensor Laboratory (Bessemer 105) for analysis according to the following protocol:

Protocol for EBC analysis – electrochemical sensor and Amplex red. To take place in Bessemer 105, Biosensor Laboratory, researchers only.

All samples will be analysed. No samples will be retained.

1. Potassium phosphate monobasic, potassium phosphate dibasic, and potassium chloride salts are added to 200 µl of EBC to make pH 7.4 0.1 M phosphate buffer with 0.1 M potassium chloride.
2. 30 µl of buffered EBC is dropped onto electrochemical sensor for hydrogen peroxide analysis.
3. 48 µl of buffered EBC is withdrawn into 96-well plates with addition of 1 µl 5 U/ml horse radish peroxidase (HRP) and 1 µl 2.5mM Amplex red solution. The 96-well plates are then incubated for 30 minutes at room temperature with platform shaker before measurement with fluorometer. The excitation and absorption wavelength of the fluorometer are set to 535 and 587 nm respectively.
4. The electrochemical analysis results are compared with the Amplex red assay. Paired *t* tests, correlation, regression and Bland-Altman analysis will be used for comparative purposes, following standard practise in analytical sciences.

PET mouthpiece sterilisation:

1. Mouthpiece is wiped with 75% ethanol before use and safely disposed of following use.

Cleaning of the Equipment & Transport of Sample

We will be following the Local Imperial College Bioengineering departmental protocol for transporting exhaled breath samples and disinfection of equipment in the document of BioSOP026:

Transport and receipt of Materials

- a) Human tissue must be transported in UN3373 compliant packaging. This packaging consists of three components.
 1. A primary receptacle: the tube, vial or other container that is in direct contact with the specimen.
 2. A secondary packaging that fully encapsulates the primary receptacle. Adsorbent material should be placed inside the secondary packaging in case the primary receptacle leaks.
 3. An outer packaging for shipping or transit.

Designated couriers should transport the tissue to Imperial College. For example, CitySprint can courier human tissue

Cleaning and decontamination

Following all procedures work surfaces (which should be in spill trays or biological safety cabinets) must be cleaned with 1% Virkon solution followed by soap and water, and finally 70% ethanol. Whenever practicable, small articles that have been contaminated with human tissue or body fluids should be submerged in disinfectant at the appropriate working dilution for several hours before washing. Other contaminated surfaces (e.g floor, cupboards and walls) should be washed down with disinfectant. Bench surfaces should be washed down with disinfectant at the end of every

experimental session. A discard bin containing freshly prepared disinfectant should be within easy reach on each working bench and should be clearly labelled with the type, strength and usage of the disinfectant.

Duration of Study

Overall, the study will last 12 months from advertising to the end of data collection.

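### Spirometry comes before breath collection at every visit with no stated interval, so any passing effect of it could not be separated from the within-day variability of objective 3

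*Protocol*

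**What the plan says.** Protocol section 3 (Study design) sets the order of events: "participants will perform spirometry measurements prior to the following the breath collection procedures". It adds: "These procedures will be performed on each study visit". The available text names no rest or interval between spirometry and the first collection. The sample-collection flow chart and the overview of the two evaluations are figures that are not reproduced, so they may hold timings that cannot be seen here.

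The Study tests part of section 3 then says: "The following process is repeated 3 times in total to collect 3 EBC samples per participant". Each cycle consists of bringing the device to temperature (typically 1 to 3 minutes), normal breathing for at most 5 minutes, transfer of the sample and an ethanol wipe.

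Section 2 (Study objectives) lists as its third question: "Variability between 3 samples collected in 1 day". Its fourth is: "Variability between 3 tests collected in 1st month, 2nd month and 3rd month". Its fifth asks whether a standardisation based on breath temperature and flow, measured on the device, is useful.

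Spirometry does not appear in the eligibility criteria (sections 4.2 and 4.3), the objectives (section 2) or the analysis (section 7).

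**The concern.** The three samples of one day are meant to be replicates: same person, same device, same conditions. Under the stated order they differ systematically in one condition, the time since a breathing test. The first sample is always closest to it and the third always furthest away, with no counterbalancing across participants or visits.

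The protocol itself treats collection conditions as important. In section 1.1 it remarks that "previous EBC collector designs have not considered how EBC sample composition depends on temperature and flow rate", and it attributes the wide variation between published results to that neglect. It also asks participants to breathe normally during collection. Putting another breathing test at an uncontrolled interval before the first sample sits awkwardly with that approach.

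At stake is how objective 3 is read. A passing effect of spirometry, if there is one, would be counted as within-day variability of the device. This study is meant to inform the design of later evaluations, so that estimate would be carried forward.

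**Working it through.** The protocol gives no sample size calculation, variance or effect of spirometry, so there is no figure of its own to reproduce. The check has three parts.

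**1. Is time since spirometry tied to sample order?** Let *t* be the unstated interval from spirometry to the start of sample 1. One cycle takes about 1 + 3 = 4 minutes (shortest warm-up, and the shortest collection time in objective 1) to 3 + 5 = 8 minutes (longest warm-up, longest collection), plus handling. Sample 2 therefore starts at about *t* + 4 to *t* + 8 minutes, and sample 3 at about *t* + 8 to *t* + 16 minutes. The order is the same in all 30 participants (15 with COPD, 15 healthy) at all three visits. Time since spirometry always rises with sample number.

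**2. What would a passing effect do to the within-day CV?** Assumptions, none of them from the protocol: the effect shifts sample 1 by a fraction *e* of the mean and halves at each later sample, so the shifts are (*e*, *e*/2, *e*/4); the CV without the effect is 10%, 20% or 30%.

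- Mean shift: (1 + 0.5 + 0.25)*e*/3 = 0.5833*e*.
- Sample variance of the shifts: [(0.4167)² + (−0.0833)² + (−0.3333)²]*e*²/2 = 0.1458*e*².
- Apparent CV = √(CV² + 0.1458*e*²). For example, with CV = 0.10 and *e* = 0.20: √(0.0100 + 0.00583) = 0.126.

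| CV without effect | *e* = 0 | *e* = 5% | *e* = 10% | *e* = 20% |
|---|---|---|---|---|
| 10% | 10.0% | 10.2% | 10.7% | 12.6% |
| 20% | 20.0% | 20.1% | 20.4% | 21.4% |
| 30% | 30.0% | 30.1% | 30.2% | 31.0% |

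A harsher shape, in which only sample 1 is shifted and recovery is complete by sample 2, has sample variance *e*²/3. From a 10% CV it gives √(0.01 + 0.10²/3) = 11.5% for *e* = 10% and √(0.01 + 0.20²/3) = 15.3% for *e* = 20%. A gradual decline is the more realistic shape, so the table is the better guide.

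**3. What does it do to the other comparisons?**

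- Month to month: if the same effect occurs at each visit, every three-sample visit mean moves by 0.5833*e*. The variance of three equal shifts is zero, so nothing is added between visits.
- Sensor against Amplex Red: both read aliquots of the same buffered condensate, so a change in the sample reaches both and their difference is not affected.

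**The case against.** The strongest reply is that no effect has been shown. Nothing in the protocol reports that spirometry alters the volume or the hydrogen peroxide of the condensate. The background remarks on temperature and flow concern conditions during collection, not earlier effort. That stands: the point is about a possible effect that the design cannot separate, not about a demonstrated one.

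A second reply is that breath temperature and flow are recorded on the device, so a change acting through them would be seen and could be corrected. This stands in part. Whether the correction works is itself objective 5, so it cannot be relied on to protect objective 3. Nor would it address a change in airway peroxide itself, although the protocol gives no evidence of one.

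A third is that an analysis could include a term for sample position. It could remove a common trend, but it would remove device drift or carry-over between collections along with any recovery from spirometry. Those device effects belong to what objective 3 should describe.

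A fourth is that section 1.2 wants reproducibility assessed in the same way as in the earlier evaluation of healthy volunteers, so reordering might cost comparability. This is fair as far as it goes; the protocol does not state the order used there.

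A reader might also infer more than the text supports:

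- **That month-to-month variability is distorted too.** Spirometry precedes collection at every visit, so a constant effect cancels. This assumes a similar interval and number of samples at each visit; the protocol gives no ground for expecting a systematic difference.
- **That visit 1 differs because "The first visit also includes screening which will take up to 1 hour".** The content described is explanation, consent and paperwork: "As part of screening, they will have a baseline screening questionnaire including a check of medications they are currently taking". No mechanism is given by which this would change the condensate.
- **That collection follows forced manoeuvres immediately.** The protocol gives only the order, and describes neither the manoeuvre nor the delay.
- **That the effect would be larger in COPD.** Nothing in the protocol says so.

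**Conclusion.** The point holds for objective 3 only. The stated order ties time since spirometry to sample number throughout the study, and any passing effect would be inseparable from within-day variability. Its size is unknown and may be zero. On the assumed halving pattern, a first-sample shift of 5% to 20% turns a 10% CV into 10.2% to 12.6%, and a 30% CV into at most 31.0%. The possible harm is therefore small to moderate, and smaller the noisier the measurement already is.

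The change is still worth making before data collection. No stated criterion, objective or analysis depends on spirometry coming first, and reordering costs almost nothing. Objective 4, the visit 1 screening and the agreement between methods are not part of the finding. The conclusion assumes that the figures not reproduced do not already fix an interval.

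**What to change.** In section 3, state that breath collection is done before spirometry at each visit, and that the start time of each of the three collections is recorded.

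If spirometry has to stay first, for example to match the first evaluation, state one fixed interval between the end of spirometry and the start of sample 1, use it at all three visits, and record it with the start times. This does not break the tie with sample order, but it keeps the timing the same across participants and visits and allows a trend to be examined against time since spirometry.

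Cost: no new procedure and no extra staff. Reordering may lose a little comparability with the first evaluation if that used the other order. Keeping spirometry first with a fixed interval would add at most the waiting time at each visit.

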DESIGN	Assessment of accuracy and precision of a novel instrument for collecting exhaled breath condensate (EBC) and analysing the levels of hydrogen peroxide.
AIMS	
(i) Assess consistency in three successive measurements at monthly intervals in individuals with COPD & healthy volunteers.(ii) Qualitative evaluation of the usability of the device and the collection protocols from participants.(iii) To collect usability feedback, in terms of how easy to use the device and to hold to breathe through the device.
OUTCOME MEASURES	
(i) Precision and accuracy of the EBC device in COPD & healthy participants. This will be assessed by comparison with the gold standard fluorometry and mass spectrometry methods.
POPULATION	COPD & Healthy subjects
DURATION	12 months

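### Sensor and Amplex Red pairs repeat within each person, but the protocol names only methods that in standard form treat pairs as independent

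*Protocol*

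**What the plan says.** The synopsis gives the outcome as "Precision and accuracy of the EBC device in COPD & healthy participants", judged against reference methods. Two places name the analysis.

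- **Section 3, Protocol for EBC analysis, step 4.** For the sensor against Amplex Red it lists paired t tests, then says "correlation, regression and Bland-Altman analysis will be used for comparative purposes, following standard practise in analytical sciences". The methods are not ranked, and repeated pairs are not mentioned.
- **Section 7.** It names Bland-Altman plots and no other method. It also gives no repeated-measures form. It says that there was no formal sample size calculation.

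On the number of pairs:

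- **Section 3, recruitment.** "We aim to recruit 15 patients with COPD and 15 healthy volunteers".
- **Section 3, visits.** There are three monthly visits, and of the spirometry and breath collection it says "These procedures will be performed on each study visit".
- **Section 2, questions 3 and 4.** "Variability between 3 samples collected in 1 day" and "Variability between 3 tests collected in 1st month, 2nd month and 3rd month".
- **Section 3, Sample collection protocol.** "Ideally, three samples per participant will be collected". The Study tests part likewise counts three samples for each participant.

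**The concern.** Paired t tests, correlation, regression and Bland-Altman limits in their textbook form assume one independent pair per person. This design gives several pairs per person on any reading. If the sensor-minus-reference difference tends to be similar within a person, for example because something in that person's condensate affects one assay, then 9 pairs from one person carry less information than 9 pairs from nine people. An analysis that ignores this makes the estimated bias and limits look more precise than 15 people per group, or 30 in all, can support.

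The methods listed also answer different questions. A paired t test addresses mean bias only. Correlation does not detect bias, and it rises when two groups with different means are combined. Neither measures agreement, which is what the outcome asks about. What is at stake is the reported precision of the accuracy results and how they are read.

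**Working it through.** The protocol states no alpha, margin, ICC or sample size calculation, so there is no figure of its own to reproduce.

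**Inputs from the protocol.** 15 people per group and 3 visits. Pairs per person, m, are 3 if three samples is the total, or 3 × 3 = 9 if it is per visit. Per group this is 15 × 3 = 45 or 15 × 9 = 135 pairs; in all, 90 or 270.

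**Assumptions.** ICC of the differences 0, 0.1, 0.3 or 0.5; normal differences; total variance 1; true bias 0; the same number of pairs from each person; all pairs pooled as independent.

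**Step 1: design effect.** DE = 1 + (m − 1) × ICC.

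- m = 9: 1, 1.8, 3.4, 5.0. Effective number of pairs, 135/DE: 135, 75, 39.7, 27.
- m = 3: 1, 1.2, 1.6, 2.0. Effective number of pairs, 45/DE: 45, 37.5, 28.1, 22.5.

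**Step 2: false rejection by the pooled paired t test.** The pooled standard error is too small by about √DE, so a nominal 5% test rejects with probability of about 2 × [1 − Φ(1.96/√DE)]. For m = 9 and ICC 0.3 this is 1.96/√3.4 = 1.063, giving 0.288. Simulation with 20,000 runs per setting gave 0.291 there. The results per group of 15 are:

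| ICC (assumed) | 0 | 0.1 | 0.3 | 0.5 |
|---|---|---|---|---|
| 9 pairs each: pooled t test rejects | 5% | 14% | 29% | 39% |
| 3 pairs each: pooled t test rejects | 5% | 7% | 12% | 17% |
| 9 pairs each: naive 95% CI for a limit covers | 95% | 91% | 80% | 68% |
| 3 pairs each: naive 95% CI for a limit covers | 94% | 93% | 90% | 86% |

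The naive interval uses the standard error s × √[1/n + 1.96²/(2(n − 1))], with n the number of pooled pairs. Results for all 30 people together are almost the same; for 9 pairs each the test rejects 5, 15, 29 and 39% of the time.

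**Step 3: the limits themselves.** The expected pooled variance is (n − DE)/(n − 1) of the true variance. In the worst case, n = 135 and DE = 5, this is 130/134 = 0.97. With n = 45 and DE = 2 it is 43/44 = 0.98. The limits therefore hardly change; the error is in p values and intervals.

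**Step 4: participant-level analysis.** A t test on participant means rejected 4.7% to 5.3% of the time in all settings. An interval for the limit from a one-way variance-components model, by the method of variance estimates recovery (MOVER), covered about 96% at 15 people.

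**Step 5: correlation across two groups.** Section 1.1 gives typical concentrations of 0.46 μM in COPD, "compared to healthy control 0.2" μM. Half the gap is 0.26/2 = 0.13. If the two methods were unrelated within each group, the combined correlation would still be 0.13²/(0.13² + SD²). For an assumed within-group SD of 0.05, 0.10, 0.15 or 0.20 μM this is 0.87, 0.63, 0.43 or 0.30.

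**The case against.** The other side has a good case. The handling of repeated pairs is commonly left to a statistical analysis plan, which may exist here. The protocol does not say that pairs will be pooled. Bland-Altman, the suitable method, is named in both places. The ICC may be near 0, because both assays use aliquots of one buffered sample, and at 0 pooling does no harm. The protocol promises no confidence interval for the limits and sets no pass rule.

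All of this stands, and it limits the weight of the point. It does not remove it: the protocol itself fixes the methods, in two places, for data that its own design makes clustered.

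Three stronger readings are tempting but are not supported.

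- **That a poor sensor would be passed as accurate.** A reader might infer that a non-significant t test and a sizeable correlation would be taken as proof of agreement. The protocol does not say so, and the planned Bland-Altman analysis would itself show limits that were too wide.
- **That step 4 contradicts section 7.** It does not; its list includes the section 7 method and adds others.
- **That bringing step 4 into line with section 7 is enough.** Section 7 mentions only plots. It names no main analysis and no repeated-measures form, so it needs the same change.

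**Conclusion.** The point holds as a matter of analysis choice, not as an error in a decision rule. The pairs are clustered on every reading of the protocol, and neither step 4 nor section 7 provides for it.

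The size depends on two things that the protocol does not state: whether pairs are pooled, and the ICC of the differences. If both go the wrong way, the pooled test of bias rejects up to about 39% of the time at 9 pairs each, or 17% at 3, over the assumed ICC range to 0.5, and naive intervals for the limits fall to about 68% or 86% coverage. If the ICC is 0 there is essentially no harm. The limits of agreement are almost unaffected in any case. The remark that the t test and correlation do not measure agreement needs no assumption about clustering.

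**What to change.** 1. In both step 4 and section 7, state that the main analysis is Bland-Altman for repeated measures: bias and 95% limits from a participant-level variance-components model, overall and for each group.
2. Take any test or confidence interval for bias from that model or from participant means.
3. Keep the paired t test and correlation as descriptive only, and keep regression as a check for proportional bias.
4. Reconcile section 2 (questions 3 and 4) with the Sample collection protocol and Study tests parts of section 3 on whether three samples are per visit or per participant. This decides the model: a visit-within-participant component can be fitted only if several samples are taken at a visit.

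The small-sample interval for the limits is the statistician's choice; MOVER is one option.

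The cost is a wording change in two places, slightly more analysis work and wider reported intervals. With MOVER at 15 people and ICC 0, 0.1, 0.3 or 0.5, the interval for a limit is 1.08, 1.29, 1.78 or 2.29 times the naive width with 9 pairs each, and 1.14, 1.20, 1.35 or 1.52 times with 3. No extra participants, samples or assays are needed.
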